# **16. ADMINISTRATIVE AND ETHICAL CONSIDERATIONS**

## **16.1. Regulatory and Ethical Compliance**

This protocol was designed and will be conducted and reported in accordance with the International Conference on Harmonization (ICH) Harmonized Tripartite Guidelines for Good Clinical Practice, the Declaration of Helsinki, and applicable federal, state, and local regulations.

## **16.2. DUHS Institutional Review Board and DCI Cancer Protocol Committee**

The protocol, informed consent form, advertising material, and additional protocol-related documents must be submitted to the DUHS Institutional Review Board (IRB) and DCI Cancer Protocol Committee (CPC) for review. The study may be initiated only after the Principal Investigator has received written and dated approval from the CPC and IRB.

The Principal Investigator must submit and obtain approval from the IRB for all subsequent protocol amendments and changes to the informed consent form. The CPC should be informed about any protocol amendments that potentially affect research design or data analysis (i.e. amendments affecting subject population, inclusion/exclusion criteria, agent administration, statistical analysis, etc.).

The Principal Investigator must obtain protocol re-approval from the IRB within 1 year of the most recent IRB approval. The Principal Investigator must also obtain protocol re-approval from the CPC within 1 year of the most recent IRB approval, for as long as the protocol remains open to subject enrollment.

### **16.3. Informed Consent**

The informed consent form must be written in a manner that is understandable to the subject population. Prior to its use, the informed consent form must be approved by the IRB.

The Principal Investigator or authorized key personnel will discuss with the potential subject the purpose of the research, methods, potential risks and benefits, subject concerns, and other study-related matters. This discussion will occur in a location that ensures subject privacy and in a manner that minimizes the possibility of coercion. Appropriate accommodations will be made available for potential subjects who cannot read or understand English or are visually impaired. Potential subjects will have the opportunity to contact the Principal investigator or authorized key personnel with questions, and will be given as much time as needed to make an informed decision about participation in the study.

Before conducting any study-specific procedures, the Principal Investigator must obtain written informed consent from the subject or a legally acceptable representative. The original informed consent form will be stored with the subject's study records, and a copy of the informed consent form will be provided to the subject. The Principal Investigator is responsible for asking the subject whether the subject wishes to notify his/her primary care physician about participation in the study. If the subject agrees to such notification, the Principal Investigator will inform the subject's primary care physician about the subject's participation in the clinical study.

### **16.4. Study Documentation**

Study documentation includes but is not limited to source documents, case report forms (CRFs), monitoring logs, appointment schedules, study team correspondence with sponsors or regulatory bodies/committees, and regulatory documents that can be found in the DCI-mandated "Regulatory Binder", which includes but is not limited to signed protocol and amendments, approved and signed informed consent forms, FDA Form 1572, CAP and CLIA laboratory certifications, and clinical supplies receipts and distribution records.

Source documents are original records that contain source data, which is all information in original records of clinical findings, observations, or other activities in a clinical trial necessary for the reconstruction and evaluation of the trial. Source documents include but are not limited to hospital records, clinical and office charts, laboratory notes, memoranda, subjects' diaries or evaluation checklists, pharmacy dispensing records, recorded data from automated instruments, copies or transcriptions certified after verification as being accurate copies, microfiches,

photographic negatives, microfilm or magnetic media, x-rays, subject files, and records kept at the pharmacy, at the laboratories and at medico-technical departments involved in the clinical trial. When possible, the original record should be retained as the source document. However, a photocopy is acceptable provided that it is a clear, legible, and an exact duplication of the original document.

An electronic case report form (eCRF) will be the primary data collection document for the study. The eCRFs will be updated within two weeks of acquisition of new source data. Only approved study staff (See Section [14.3.1](#)) are permitted to make entries, changes, or corrections in the CRF. For electronic CRFs, an audit trail will be maintained by the electronic CRF management system, Medidata Rave.

## **16.5. Privacy, Confidentiality, and Data Storage**

The Principal Investigator will ensure that subject privacy and confidentiality of the subject's data will be maintained. Research Data Security Plans (RDSPs) will be approved by the appropriate institutional Clinical Research Unit.

To protect privacy, every reasonable effort will be made to prevent undue access to subjects during the course of the study. Prospective participants will be consented in an exam room where it is just the research staff, the patient and his family, if desired. For all future visits, interactions with research staff (study doctor and study coordinators) regarding research activities will take place in a private exam room. All research related interactions with the participant will be conducted by qualified research staff who are directly involved in the conduct of the research study.

To protect confidentiality, subject files in paper format will be stored in secure cabinets under lock and key accessible only by the research staff. Subjects will be identified only by a unique study number and subject initials. Electronic records of subject data will be maintained using a dedicated database, Medidata Rave, which is housed in an encrypted and password-protected file on a secure network drive. Access to electronic databases will be managed by the PRTBTC Data Manager. Subject data may be stored temporarily on encrypted and password-protected portable memory devices such as flash drives and external hard drives, but only when absolutely necessary. Data stored on portable memory devices will be de-identified. Subject data will be deleted from the portable memory device at the earliest opportunity. The security and viability of the IT infrastructure will be managed by the DCI and/or Duke Medicine.

Upon completion of the study, research records will be archived and handled per DUHS HRPP policy.

Subject names or identifiers will not be used in reports, presentations at scientific meetings, or publications in scientific journals.

## **16.6. Data and Safety Monitoring**

Data and Safety Monitoring will be performed in accordance with the DCI Data and Safety Monitoring Plan. For a more detailed description of the DSMP for this protocol, refer to Section 13 (Section 13.6 in particular) and Section 14.

## **16.7. Protocol Amendments**

All protocol amendments must be initiated by the Principal Investigator and approved by the IRB prior to implementation. IRB approval is not required for protocol changes that occur to protect the safety of a subject from an immediate hazard. However, the Principal Investigator must inform the IRB and all other applicable regulatory agencies of such action immediately.

Though not yet required, the CPC should be informed about any protocol amendments that potentially affect research design or data analysis (i.e. amendments affecting subject population, inclusion/exclusion criteria, agent administration, etc.).

## **16.8. Records Retention**

The Principal Investigator will maintain study-related records for the longer of a period of:

- at least two years after the date on which a New Drug Application is approved by the FDA (if an IND is involved)
- at least two years after formal withdrawal of the IND associated with this protocol (if an IND is involved)
- at least six years after study completion (Duke policy)

## 18. APPENDICES

### 18.1. Nivolumab Safety Algorithms

**Table 2: GI Adverse Event Management Algorithm.** Rule out non-inflammatory causes. If non-inflammatory cause is identified, treat accordingly and continue I-O therapy. Opiates/narcotics may mask symptoms of perforation. Infliximab should not be used in cases of perforation or sepsis.

Grade of Diarrhea/Colitis	Management	Follow-up
Grade 1 Diarrhea:< 4 stools/day over baseline; Colitis: asymptomatic	
 
Continue I-O therapy per protocol
 
Symptomatic treatment
 
	
 
Close monitoring for worsening symptoms.
 
Educate patient to report worsening immediately
 
 
If worsens:
 
 
Treat as Grade 2 or 3/4
 

Grade 2 Diarrhea: 4-6 stools per day over baseline; IV fluids indicated <24 hrs; not interfering with ADL Colitis: abdominal pain; blood in stool	
 
Delay I-O therapy per protocol
 
Symptomatic treatment
 
	
If improves to grade 1:
 
 
Resume I-O therapy per protocol
 
 
If persists > 5-7 days or recur:
 
 
0.5-1.0 mg/kg/day methylprednisolone or oral equivalent
 
When symptoms improve to grade 1, taper steroids over at least 1 month, consider prophylactic antibiotics for opportunistic infections, and resume I-O therapy per protocol.
 
 
If worsens or persists > 3-5 days with oral steroids:
 
 
Treat as grade 3/4
 

Grade 3-4 Diarrhea (G3): $\geq 7$ stools per day over baseline; incontinence; IV fluids $\geq 24$ hrs; interfering with ADL Colitis (G3): severe abdominal pain, medical intervention indicated, peritoneal signs G4: life-threatening, perforation	
 
Discontinue I-O therapy per protocol
 
1.0 to 2.0 mg/kg/day methylprednisolone IV or IV equivalent
 
Add prophylactic antibiotics for opportunistic infections
 
Consider lower endoscopy
 
	
If improves:
 
 
Continue steroids until grade 1, then taper over at least 1 month
 
 
If persists > 3-5 days, or recurs after improvement:
 
 
Add infliximab 5 mg/kg (if no contraindication). Note: Infliximab should not be used in cases of perforation or sepsis
 

Patients on IV steroids may be switched to an equivalent dose of oral corticosteroids (e.g. prednisone) at start of tapering or earlier, once sustained clinical improvement is observed. Lower bioavailability of oral corticosteroids should be taken into account when switching to the equivalent dose of oral corticosteroids.

**Table 3: Renal Adverse Event Management Algorithm.** Rule out non-inflammatory causes. If non-inflammatory cause, treat accordingly and continue I-O therapy.

Grade of Creatinine Elevation	Management	Follow-up
Grade 1 Creatinine > ULN and > than baseline but ≤ 1.5x baseline	
 
Continue I-O therapy per protocol
 
Monitor creatinine weekly
 
	If returns to baseline: 
 
Resume routine creatinine monitoring per protocol
 
 If worsens: 
 
Treat as Grade 2 or 3/4
 

Grade 2-3 Creatinine > 1.5x baseline to ≤ 6x ULN	
 
Delay I-O therapy per protocol
 
Monitor creatinine every 2-3 days
 
0.5 to 1.0 mg/kg/day methylprednisolone IV or oral equivalent
 
Consider renal biopsy with nephrology consult
 
	If returns to grade 1: 
 
Taper steroids over at least 1 month, consider prophylactic antibiotics for opportunistic infections, and resume I-O therapy and routine creatinine monitoring per protocol
 
 If elevations persists > 7 days or worsen: 
 
Treat as Grade 4
 

Grade 4 Creatinine > 6x ULN	
 
Discontinue I-O therapy per protocol
 
Monitor creatinine daily
 
1.0 to 2.0 mg/kg/day methylprednisolone IV or IV equivalent
 
Consult nephrologist
 
Consider renal biopsy
 
	If returns to grade 1: 
 
Taper steroids over at least 1 month and add prophylactic antibiotics for opportunistic infections
 

Patients on IV steroids may be switched to an equivalent dose of oral corticosteroids (e.g. prednisone) at start of tapering or earlier, once sustained clinical improvement is observed. Lower bioavailability of oral corticosteroids should be taken into account when switching to the equivalent dose of oral corticosteroids.

**Table 4: Pulmonary Adverse Event Management Algorithm.** Rule out non-inflammatory causes. If non-inflammatory cause, treat accordingly and continue I-O therapy. Evaluate with imaging and pulmonary consultation.

Grade of Pneumonitis	Management	Follow-up
Grade 1 Radiographic changes only	
 
Consider delay of I-O therapy
 
Monitor for symptoms every 2-3 days
 
Consider Pulmonary and ID consults
 
	
 
Re-image at least every 3 weeks
 
 
If worsens:
 
 
Treat as Grade 2 or 3-4
 

Grade 2-3 Mild to moderate new symptoms	
 
Delay I-O therapy per protocol
 
Pulmonary and ID consults
 
Monitor symptoms daily, consider hospitalization
 
1.0 mg/kg/day methylprednisolone IV or oral equivalent
 
Consider bronchoscopy, lung biopsy
 
	
 
Re-image every 1-3 days
 
 
If improves:
 
 
When symptoms return to near baseline, taper steroids over at least 1 month and then resume I-O therapy per protocol and consider prophylactic antibiotics
 
 
If not improving after 2 weeks or worsening:
 
 
Treat as Grade 3-4
 

Grade 4 Severe new symptoms; New/worsening hypoxia; Life-threatening	
 
Discontinue I-O therapy per protocol
 
Hospitalize
 
Pulmonary and ID consults
 
2-4 mg/kg/day methylprednisolone IV or IV equivalent
 
Add prophylactic antibiotics for opportunistic infections
 
Consider bronchoscopy, lung biopsy
 
	
If improves to baseline:
 
 
Taper steroids over at least 6 weeks
 
 
If not improving after 48 hours or worsening:
 
 
Add additional immunosuppression
 

Patients on IV steroids may be switched to an equivalent dose of oral corticosteroids (e.g. prednisone) at start of tapering or earlier, once sustained clinical improvement is observed. Lower bioavailability of oral corticosteroids should be taken into account when switching to the equivalent dose of oral corticosteroids.

**Table 5: Hepatic Adverse Event Management Algorithm.** Rule out non-inflammatory causes. If non-inflammatory cause, treat accordingly and continue I-O therapy. Consider imaging for obstruction.

Grade of Liver Test Elevation	Management	Follow-up
Grade 1 AST or ALT > ULN to 3.0 x ULN and/or T. bili > ULN to 1.5 x ULN	
 
Continue I-O therapy per protocol
 
	
 
Continue LFT monitoring per protocol
 
 
If worsens:
 
 
Treat as Grade 2 or 3-4
 

Grade 2 AST or ALT > 3.0 to ≤ 5 x ULN and/or T. bili > 1.5 to ≤ 3 x ULN	
 
Delay I-O therapy per protocol
 
Increase frequency of monitoring to every 3 days
 
	
If returns to baseline:
 
 
Resume routine monitoring, resume I-O therapy per protocol
 
 
If elevation persists > 5-7 days or worsens:
 
 
0.5-1 mg/kg/day methylprednisolone or oral equivalent and when LFT returns to grade 1 or baseline, taper steroids over at least 1 month, consider prophylactic antibiotics for opportunistic infections, and resume I-O therapy per protocol
 

Grade 3-4 AST or ALT > 5 x ULT or T. bili > 3 x ULN	
 
Discontinue I-O therapy per protocol*
 
Increase frequency of monitoring to every 1-2 days
 
1.0 to 2.0 mg/kg/day methylprednisolone IV or IV equivalent*
 
Add prophylactic antibiotics for opportunistic infections
 
Consult gastroenterologist
 
	
If returns to Grade 2:
 
 
Taper steroids over at least 1 month
 
 
If does not improve in >3-5 days, worsens or rebounds:
 
 
Add mycophenolate mofetil 1 g BID
 
If no response within an additional 3-5 days, consider other immunosuppressants per local guidelines
 

Patients on IV steroids may be switched to an equivalent dose of oral corticosteroids (e.g. prednisone) at start of tapering or earlier, once sustained clinical improvement is observed. Lower bioavailability of oral corticosteroids should be taken into account when switching to the equivalent dose of oral corticosteroids.

\*The recommended starting dose for grade 4 hepatitis is 2 mg/kg/day methylprednisolone IV.

**Table 6: Endocrinopathy Adverse Event Management Algorithm.** Rule out non-inflammatory causes. If non-inflammatory cause, treat accordingly and continue I-O therapy. Consider visual field testing, endocrinology consultation, and imaging.

Asymptomatic TSH Elevation	
 
Continue I-O therapy per protocol
 
If TSH < 0.5 x LLN, or TSH > 2 x ULN, or consistently out of range in 2 subsequent measurements: include fT4 at subsequent cycles as clinically indicated; consider endocrinology consult
 
	
Symptomatic endocrinopathy	
 
Evaluate endocrine function
 
Consider pituitary scan
 
 
Symptomatic with abnormal lab/pituitary scan:
 
 
Delay I-O therapy per protocol
 
1-2 mg/kg/day methylprednisolone IV or PO equivalent
 
Initiate appropriate hormone therapy
 
 
No abnormal lab/pituitary MRI scan but symptoms persist:
 
 
Repeat labs in 1-3 weeks / MRI in 1 month
 
	
If improves (with or without hormone replacement):
 
 
Taper steroids over at least 1 month and consider prophylactic antibiotics for opportunistic infections
 
Resume I-O therapy per protocol
 
Patients with adrenal insufficiency may need to continue steroids with mineralocorticoid component
 

Suspicion of adrenal crisis (e.g., severe dehydration, hypotension, shock out of proportion to current illness)	
 
Delay or discontinue I-O therapy per protocol
 
Rule out sepsis
 
Stress dose of IV steroids with mineralocorticoid activity
 
IV fluids
 
Consult endocrinologist
 
If adrenal crisis ruled out, then treat as above for symptomatic endocrinopathy
 
	

Patients on IV steroids may be switched to an equivalent dose of oral corticosteroids (e.g. prednisone) at start of tapering or earlier, once sustained clinical improvement is observed. Lower bioavailability of oral corticosteroids should be taken into account when switching to the equivalent dose of oral corticosteroids.

**Table 7: Skin Adverse Event Management Algorithm.** Rule out non-inflammatory causes. If non-inflammatory cause, treat accordingly and continue I-O therapy.

Grade of Rash	Management	Follow-up
Grade 1-2 Covering ≤ 30% BSA*	
 
Symptomatic therapy (e.g., antihistamines, topical steroids)
 
Continue I-O therapy per protocol
 
	If persists > 1-2 weeks or recurs: 
 
Consider skin biopsy
 
Delay I-O therapy per protocol
 
Consider 0.5-1.0 mg/kg/day methylprednisolone IV or oral equivalent. Once improving, taper steroids over at least 1 month, consider prophylactic antibiotics for opportunistic infections, and resume I-O therapy per protocol
 
 If worsens: 
 
Treat as Grade 3-4
 

Grade 3-4 Covering > 30% BSA; Life threatening consequences * ^	
 
Delay or discontinue I-O therapy per protocol
 
Consider skin biopsy
 
Dermatology consult
 
1.0-2.0 mg/kg/day IV methylprednisolone IV or IV equivalent
 
	If improves to Grade 1: 
 
Taper steroids over at least 1 month and add prophylactic antibiotics for opportunistic infections
 
Resume I-O therapy per protocol.
 

Patients on IV steroids may be switched to an equivalent dose of oral corticosteroids (e.g. prednisone) at start of tapering or earlier, once sustained clinical improvement is observed. Lower bioavailability of oral corticosteroids should be taken into account when switching to the equivalent dose of oral corticosteroids.

\*Refer to NCI CTCAE v4 for term-specific grading criteria

^If SJS/TEN is suspected, withhold I-O therapy and refer patient for specialized care for assessment and treatment. If SJS or TEN is diagnosed, permanently discontinue I-O therapy.

**Table 8: Neurological Adverse Event Management Algorithm.** Rule out non-inflammatory causes. If non-inflammatory cause, treat accordingly and continue I-O therapy.

Grade of Neurological Toxicity	Management	Follow-up
Grade 1 Asymptomatic or mild symptoms; Intervention not indicated	
 
Continue I-O therapy per protocol
 
	
 
Continue to monitor the patient
 
 If worsens: 
 
Treat as Grade 2 or 3-4
 

Grade 2 Moderate symptoms; Limiting instrumental ADL	
 
Delay I-O therapy per protocol
 
Treat symptoms per local guidelines
 
Consider 0.5 to 1.0 mg/kg/day methylprednisolone IV or PO equivalent
 
	If improves to baseline: 
 
Resume I-O therapy per protocol when improved to baseline
 
 If worsens: 
 
Treat as Grade 3-4
 

Grade 3-4 Severe symptoms; Limiting self-care ADL; Life-threatening	
 
Discontinue I-O therapy per protocol
 
Obtain neurology consult
 
Treat symptoms per local guidelines
 
1.0-2.0 mg/kg/day IV methylprednisolone IV or IV equivalent
 
Add prophylactic antibiotics for opportunistic infections
 
	If improves to Grade 2: 
 
Taper steroids over at least 1 month
 
 If worsens or atypical presentation: 
 
Consider IVIG or other immunosuppressive therapies per local guidelines
 

Patients on IV steroids may be switched to an equivalent dose of oral corticosteroids (e.g. prednisone) at start of tapering or earlier, once sustained clinical improvement is observed. Lower bioavailability of oral corticosteroids should be taken into account when switching to the equivalent dose of oral corticosteroids.

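### Table 4 (pneumonitis) labels its mild-to-moderate row Grade 2-3 and its severe row Grade 4 only, while its own cross-references point to a Grade 3-4 row that does not exist

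*Combined protocol and SAP*

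**What the plan says.** Sections 9.1.3 and 13.1 send the reader to Section 18.1 for managing nivolumab toxicity, so Table 4 is working guidance for pneumonitis. It has three rows.

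- **Grade 1:** radiographic changes only. On worsening, the instruction is "Treat as Grade 2 or 3-4".
- **Grade 2-3:** "Mild to moderate new symptoms". The steroid is "1.0 mg/kg/day methylprednisolone IV or oral equivalent". The escalation condition is "If not improving after 2 weeks or worsening", and the action is then "Treat as Grade 3-4".
- **Grade 4:** "Severe new symptoms; New/worsening hypoxia; Life-threatening". The steroid is "2-4 mg/kg/day methylprednisolone IV or IV equivalent", and admission is required.

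No row is labelled Grade 2 alone, and none is labelled Grade 3-4. None of the ipilimumab algorithms (Section 18.2, Tables 10 to 14) covers pneumonitis.

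**The concern.** A Grade 3 pneumonitis belongs in the middle row if the clinician goes by the printed grade. It belongs in the last row if the clinician goes by the symptom description or the cross-references. The escalation step is also circular for a Grade 3 patient placed by label: the patient is already in a row that includes Grade 3 and is told to be treated as Grade 3-4.

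At stake is the treatment of a toxicity that is already present. The single-dose design makes the instructions to delay, resume or stop immunotherapy largely moot. Steroid dose, admission, antibiotic cover and taper still apply.

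**Working it through.** No sample size, power or error-rate figure bears on this point. The check sets the text side by side, with one ratio.

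**Step 1. What a Grade 3 case receives under each reading of Table 4.**

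| Element | By row label (Grade 2-3 row) | By description and cross-reference (last row) |
|---|---|---|
| Methylprednisolone | 1.0 mg/kg/day, IV or oral | 2-4 mg/kg/day, IV |
| Admission | to be considered | required |
| Prophylactic antibiotics | to be considered | added |
| Steroid taper | at least 1 month | at least 6 weeks |
| Step up if not improving | after 2 weeks | after 48 hours |
| Step up if worsening | yes, no waiting period | yes, no waiting period |

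Ratio of starting doses: 2 / 1.0 = 2 at the lower end and 4 / 1.0 = 4 at the upper end.

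**Step 2. Which element of Table 4 is out of line.**

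- *Cross-references.* The wording "Treat as Grade 2 or 3-4" also appears in Tables 5 and 8. Both of those tables have the Grade 2 and Grade 3-4 rows it names; Table 4 does not.
- *Descriptions.* Table 8 labels the row "Severe symptoms; Limiting self-care ADL; Life-threatening" as Grade 3-4. Table 9 defines Grade 3 myocarditis as severe. In Table 4 the severe row is labelled Grade 4 only.
- *Severity scale.* Section 13.1 equates moderate with 2, severe with 3 and life-threatening with 4. That scale applies formally only to events without CTCAE grading, so it is supporting evidence.

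**Step 3. Row groupings across the appendix.** Tables 2 to 14 are 13 algorithms. Tables 6 and 12 use no grades, which leaves 13 − 2 = 11.

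- Grade 3 shares a row with Grade 4 in 9 of 11: Tables 2, 5, 7, 8, 9, 10, 11, 13 and 14.
- Grade 3 shares a row with Grade 2 in 2 of 11: Tables 3 and 4.

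Table 3 (renal) can be followed as printed, because creatinine limits fix each row and its Grade 2-3 row escalates to Grade 4. Table 4 has no numeric limits, and its escalation target overlaps its own label.

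**Result.** The cross-references, the descriptions and the usual pattern of the appendix all place Grade 3 in the last row. Only the two labels disagree.

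**The case against.** The strongest reply is that a treating physician reads the symptom description and not just the grade number. A severely ill or hypoxic patient fits only the last row, and the neighbouring tables and Section 13.1 support that choice. On this view the intended reading can be recovered, and the fault is clerical.

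There are also safeguards. The table calls for imaging and pulmonary consultation at every grade. Both symptomatic rows require pulmonary and infectious-disease consults. The Grade 2-3 row has daily symptom monitoring, repeat imaging every 1-3 days and escalation on worsening, so only a patient who neither improves nor worsens could stay on the lower dose for 2 weeks. Exposure is small: up to 20 patients and one dose of each drug. Section 9.1.3 lists pneumonitis among the less common nivolumab effects and acute lung injury among the rare ones, and Section 11.2 excludes patients with a history of pneumonitis.

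All of this stands, and it limits how often harm could follow. It does not remove the contradiction. Events are graded by CTCAE number under Section 13.1, so looking up a row by number is a natural use of the table, and that use leads to the weaker treatment. That the intended row can be worked out from other tables is a reason to correct the labels.

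**Conclusion.** The concern holds. Table 4 is wrong as written: its last two row labels contradict both the row descriptions and both cross-references. Followed by label, a Grade 3 pneumonitis starts on one half to one quarter of the steroid dose that the rest of the table indicates, with admission and antibiotics left optional and a shorter minimum taper.

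This rests on two assumptions. The printed labels are taken to match the extracted text; extraction error is unlikely, because labels and cross-references are both clean and conflict in wording, but the PDF page itself was not seen. The intended row for Grade 3 is inferred from the descriptions, the cross-references and the other tables, so the clinical team must confirm it.

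The expected number of cases is low, and the documents give no pneumonitis rate for the combination. No endpoint, analysis set, sample size or statistical result changes. It should be fixed because the table directs treatment of a potentially serious toxicity and the error runs towards under-treatment.

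**What to change.** In Section 18.1, Table 4, relabel the row now marked Grade 2-3 as Grade 2 and the row now marked Grade 4 as Grade 3-4, once the clinical team has confirmed the intent. Both existing cross-references then resolve without further edits, and the rows match the Grade 2 and Grade 3-4 structure of Tables 2, 5 and 8.

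The cost is two row labels in the next amendment, with no effect on design or analysis. The Grade 1 cross-reference in Table 3 is also loosely worded and could be aligned with that table's Grade 2-3 and Grade 4 rows at the same time. That is optional tidying, since no renal treatment changes.
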